## 7.6 Safety Variables and Analyses

Safety Analysis will be performed using the Safety Analysis Set (Section Error! Reference source not found.). Safety is assessed by subject-reported and investigator-observed AEs, along with physical examinations, clinical laboratory tests (hematology, coagulation, chemistries, and urinalysis), vital signs, concomitant medications, ECOG performance status, and ECGs. Exposure to study drug, TEAEs, deaths, and causes of deaths will be tabulated.

## 7.6.1 Study Treatment and Exposure

Study drug administration will be summarized by numbers of treatment cycles received, delayed and dose-reduced cycles, as well as duration of exposure (in months). These measures of exposure will be based on dose administrations, dose reductions, dose interruptions and dose delays identified by the investigator and collected on the study drug administration eCRFs. Duration of exposure, in months, is defined as the last treatment date minus the first date of treatment + 1 divided by 30.4375.

Summaries of delayed, dose interrupted, and dose reduced cycles will be provided at both subject and cycle levels.

Dose intensity, presented as the incidence of subjects receiving <80% of their intended dose, will be summarized by cycle. Dose intensity will be calculated as the actual total dose divided by planned total dose for each treatment cycle.

Both completed or partially completed dose cycles are counted in these summaries.

#### 7.6.2 Adverse Events

Adverse events reported by study subjects or observed by investigators will be mapped to the appropriate System Organ Class (SOC) and Preferred Term (PT) according to the Medical Dictionary for Regulatory Activities (MedDRA). Severity of AEs will be graded using Common Terminology Criteria for Adverse Events (CTCAE) version 4.03 (protocol Appendix 2).

TEAEs are defined as events that first occurred or worsened on or after the date of the first dose of study treatment until 30 days after the last dose of study treatment or until the start of a post-treatment alternative anti-cancer treatment, whichever occurs first, with the following exceptions: events that occurred after 30 days beyond the last dose of study treatment or the start of a post-treatment alternative anti-cancer treatment will also be considered treatment-emergent if the events are both serious and related to the study treatment. For the purpose of determining whether an AE is a TEAE, incomplete AE start and stop dates will be imputed conservatively following the data programming conventions as detailed in the Taiho Data Programming Standards.

All AE data collected in the study database with an AE start date on or before the data cutoff date will be included in the data listings, including those that are not treatment emergent. Only TEAEs will be included in the AE summary tables.

An overall safety summary table containing counts and percentages of subjects with any AE, any AE Grade ≥3, AE leading to treatment discontinuation, any SAE, and subcategories of SAEs (fatal SAEs) will be produced.

Related events are those that the Investigator considered to be related to study treatment as described in the study protocol. All summaries of AEs will be summarized by cohorts and all cohorts combined within regimen within parts (A&B), and within Phase (I&II). Tables may be combined when space allows.

## For example,

- Phase 1A: Cohort 1, Cohort 2, ..., Cohort n
- Phase 1B powder in bottle and tablets
- Phase 2: Cohort A, Cohort B, ..., Cohort F
- Phase 1A, Phase 1B, and Phase 2

The number and percentage of subjects experiencing AEs will be summarized by MedDRA SOCs (sorted alphabetically) with PTs sorted alphabetically within each SOC. The number and percentage of subjects experiencing AEs will also be summarized by PT and sorted by event frequency of the Total column. Related AEs, SAEs, and related SAEs will be summarized similarly. A summary of AEs with fatal outcomes, AEs resulting in permanent treatment discontinuation, and AEs resulting in treatment delay, interruption or dose reduction will also be provided. Additional summaries will be generated by SOC, PT and CTCAE grade. For these summaries, if the occurrence of a particular AE for a given subject is reported more than once, the event is only counted once with its worst CTCAE grade.

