1.5. Potential Risks and Benefits to Human Subjects

The MAPK pathway is a key regulator of cellular proliferation and survival. Somatic alterations in MAPK pathway components that deregulate the pathway are highly prevalent in human cancer (Santarpia et al 2012; Kim and Choi 2010; Dhillon et al 2010; Roberts and Der 2007). Agents targeting the MAPK pathway (eg, BRAF and MEK inhibitors) have demonstrated clinical efficacy and have attained regulatory approval for BRAF-mutated metastatic melanoma (Bollag et al 2012) and BRAF mutated NSCLC (FDA 2017). Recently, several ERK inhibitors have entered clinical testing (https://clinicaltrials.gov/); however, none have yet attained regulatory approval.

In the FIH Phase 1-2 trial of the ERK inhibitor ulixertinib at oral doses up to 900 mg administered twice a day (BID), treatment-related dose limiting toxicities (DLTs) included Grade 3 rash, Grade 3 pruritus, Grade 3 aspartate aminotransferase (AST) elevation, Grade 3 and Grade 2 diarrhea, Grade 3 vomiting, Grade 3 dehydration, Grade 3 elevated creatinine, and Grade 2 hypotension. At the recommended Phase 2 dose (RP2D) of 600 mg BID, ulixertinib was commonly associated with cutaneous adverse events (AEs) (rash, pruritus, dermatitis acneiform, and dry skin), GI AEs (diarrhea, nausea, and vomiting), decreased appetite, fatigue, and peripheral edema (Sullivan et al 2018; Li et al presentation 2017; Infante et al abstract 2015; Infante et al presentation 2015), with 32% of subjects requiring dose reductions. One event each of retinal vein occlusion (RVO) and cardiac failure and 2 events of acute renal failure were reported. Responses were observed in subjects with typical and atypical BRAF mutations and NRAS mutations.

In an FIH Phase 1 trial of another ERK inhibitor, GDC-0994 at oral doses up to 800 mg once a day for the first 21 days of a 28-day cycle, was associated with rash, diarrhea, visual disturbances, and asymptomatic LVEF decrease. At the RP2D of 400 mg, GDC-0994 was commonly associated with cutaneous AEs (rash, dry skin, and dermatitis acneiform); GI AEs (diarrhea, nausea, and vomiting), decreased appetite, fatigue, visual disturbances (blurred vision) and peripheral and periorbital edema (Varga et al 2020). Responses were observed in 2 subjects with CRC and BRAF mutations.

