7.1.7. Transition From Fed to Fasted Administration

At the time of Amendment 2.0, dose escalation (Phase 1 Part A) was ongoing. In Phase 1 Part A, ASXT029-01 dose was escalated in sequential cohorts from 10 mg/day to 200 mg/day QD using the PiB form in fed subjects. One DLT (Grade 3 nonserious maculo-papular rash) was reported in the 200-mg/day PiB cohort. Six subjects were enrolled in the tablet-bridging cohort at 80 mg/day QD under fed conditions with no DLTs being reported, and enrollment was ongoing in the 120-mg/day QD tablet cohort.

Preliminary PK data at the time of Amendment 2.0, showed relatively high variability for systemic exposures after ASTX029 was dosed with food. The geometric mean (CV%) plasma AUC_{0-inf} values on C1D1 were 2377(170) ng•h/mL for the 80-mg tablet-bridging cohort (n=4), compared with 4053(83) ng•h/mL for the 120 mg PiB (n=5) cohort and 8304(53) ng•h/mL for the 200 mg PiB cohort (n=9).

With Protocol Amendment 2.0, administration under fasted conditions was introduced. Fasted administration may result in higher exposure of ASTX029 at lower doses (Section 1.3.2.1) and potentially reduce intersubject variability compared with administration with food.

Transition to fasted-state dosing occurred during Phase 1 Part A by dosing a bridging cohort of 3 subjects at a dose of 40 mg/day tablets QD. Starting with Amendment 3.0, dose escalation under fed conditions was discontinued, and dose escalation under fasted conditions is ongoing. Please refer to the current ASTX029 IB for preliminary PK and safety data.

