7.7. Overdose Instructions

Record the actual dose of study drug administered in the source document and on the Dosing eCRF. Record any adverse clinical signs and symptoms associated with a potential overdose on the AE eCRFs. Report signs and symptoms of a potential overdose that meet SAE criteria

(defined in Section 10.1.2) to the Sponsor's Pharmacovigilance group or its designee within 24 hours from the time the investigator first becomes aware of the SAE (see Section 10.2.4). Treat any AE (including SAE) based on standard care for the specific signs and symptoms.

8. **RISKS/PRECAUTIONS**

Refer to the ASTX029 IB for the most current risks and precautions, as well as a list of potential AEs associated with ASTX029 therapy based on nonclinical toxicology studies and clinical findings with other investigational agents in this drug class.

This study represents the first use of ASTX029 in humans, and as with any investigational medicinal product (IMP), subjects may experience reactions or complications that are unknown and therefore unpredictable. Risks to subjects participating in this first evaluation of ASTX029 in a human clinical trial include the potential for adverse reactions.

Based on nonclinical toxicology studies with this molecule, and clinical findings with other investigational agents in this drug class (ERK inhibitors; ie, ulixertinib and GDC-0994) (Sullivan et al 2018; Li et al presentation 2017; Varga et al 2020; Infante et al abstract 2015; Infante et al presentation 2015), the ASTX029 mechanism of action may result in cutaneous AEs (eg, rash, pruritus, dry skin), GI AEs (eg, diarrhea, nausea, vomiting, and esophagitis), fatigue, peripheral and periorbital edema, LVEF decrease, potential arrhythmias, visual disturbances, and liver enzyme elevation.

The potential for these AEs warrants frequent monitoring of subjects participating in clinical trials of ASTX029 until the safety profile is further understood. In particular, clinical signs and/or symptoms of cutaneous, ocular, GI, and liver toxicities and LVEF decrease will be closely monitored, evaluated, and managed during the study (Appendix 4, Appendix 5, Appendix 6, Appendix 7, and Appendix 8 respectively).

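### SAP 7.6.2 prespecifies no subject-level rate or worst grade for rash as a group; a grouped rash row with its term list fixed in advance would supply one

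*SAP*

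**What the plan says.** SAP 7.6.2 sets out the adverse event displays. The main table is described as follows: "The number and percentage of subjects experiencing AEs will be summarized by MedDRA SOCs (sorted alphabetically) with PTs sorted alphabetically within each SOC". A second table drops the SOC level: "The number and percentage of subjects experiencing AEs will also be summarized by PT and sorted by event frequency of the Total column". Other event classes follow the same layout: "Related AEs, SAEs, and related SAEs will be summarized similarly". For severity, "Additional summaries will be generated by SOC, PT and CTCAE grade"; in those tables a given event reported repeatedly by one subject counts once, at its worst grade. The section also plans a high-level table, "An overall safety summary table containing counts and percentages of subjects with any AE" and a few further categories, none of them a type of toxicity. It plans summaries of events that were fatal, that led to permanent discontinuation, or that led to delay, interruption or dose reduction. Protocol 11.7 likewise stops at SOC and PT. Neither document defines a grouped term, a standardised MedDRA query or an adverse event of special interest.

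Protocol Section 8 names the toxicities of most interest: "clinical signs and/or symptoms of cutaneous, ocular, GI, and liver toxicities and LVEF decrease will be closely monitored, evaluated, and managed during the study". Protocol 1.5 describes the experience with another ERK inhibitor as "cutaneous adverse events (AEs) (rash, pruritus, dermatitis acneiform, and dry skin" and further events. Protocol 7.1.7 records for this trial: "One DLT (Grade 3 nonserious maculo-papular rash) was reported in the 200-mg/day PiB cohort". Appendix 4 (Table 15) distinguishes acneiform papulopustular rash from maculopapular rash.

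**The concern.** Rash is a foreseeable toxicity of this drug class, and the protocol already describes it under at least three names. If those names code to separate PTs, each PT row shows only part of the affected subjects. The SOC row goes too far the other way, because it also takes in dry skin, pruritus and any other skin disorder. How many subjects had any rash, and how severe was it at worst, falls between the two levels.

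Safety is the primary objective of Phase 1, so this question will be asked. The subject listings would allow the answer to be assembled later, but the choice of which terms count as rash would then be made with open-label data in view. The frequency-sorted PT table has a related weakness: a toxicity recorded under several terms ranks below an equally common one recorded under a single term.

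**Working it through.** **Inputs from the documents.** Part B has 14 subjects per dose or regimen, and the plan states a 90% chance of seeing at least one adverse reaction of 15% incidence (Protocol 11.1, SAP 4.0). A Phase 2 cohort has up to 29 subjects.

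**Assumptions, not in the documents.** Three rash terms code to three separate PTs. The row counts and PT rates below are illustrative.

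**1. The plan's own figure.** 1 − 0.85^14 = 0.897, which agrees with the stated 90%.

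**2. The same 15% toxicity split over PTs.** With k equal, non-overlapping PTs, each has rate 0.15/k, and the chance that a given row shows at least one subject among 14 is 1 − (1 − 0.15/k)^14.
- k = 2: 1 − 0.925^14 = 0.664
- k = 3: 1 − 0.95^14 = 0.512

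The chance of at least one event somewhere in the table remains 0.897. Nothing is lost from the data; what is diluted is the single row a reader looks at.

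**3. What PT rows say about subjects affected.** A subject may appear in more than one PT row. Hence the number affected is at least the largest row and at most the smaller of the row sum and N.
- Rows 3, 2, 2 of 14: from 3 (3/14 = 21%) to 3 + 2 + 2 = 7 (7/14 = 50%).
- Rows 6, 5, 4 of 29: from 6 (6/29 = 21%) to 6 + 5 + 4 = 15 (15/29 = 52%).

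**4. Range over assumed rates.** With three PTs at 15% to 25% each, the largest row shows 15% to 25%. The proportion with any rash is:
- full overlap: 15% to 25%
- independence, 1 − (1 − p)^3: 39% to 58%
- one term per subject, 3p: 45% to 75%

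**5. Worst grade.** The worst-grade rule applies within a given event. If three different subjects in a cohort of 29 each have one Grade 3 event under a different term, the grouped rate is 3/29 = 10.3%. The table shows three rows of 1/29 = 3.4%.

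**The case against.** The strongest reply is that the protocol's own category is the broad one. It speaks of cutaneous toxicity, counts pruritus and dry skin within it, and writes its DLT criterion and Appendix 4 for skin toxicity as a whole. The skin SOC row already gives a subject count for roughly that category, by grade. This stands. A reader might infer that no table gives the number of subjects affected; for cutaneous toxicity taken broadly that is untrue. The gap concerns rash only.

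A reader might also infer that the rash rate cannot be read from any planned table. SAP 1.0 places the table specifications in a separate document, which was not available, so a grouped row there cannot be excluded. The SAP text simply does not call for one.

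A third tempting inference is that rash drives dose changes at the recommended Phase 2 dose. The documents do not show this. The single reported rash DLT dates from Amendment 2.0, with the powder formulation given with food. That formulation has been phased out, and the recommended dose is taken fasted. The dermatitis acneiform reports in Protocol 1.5 come from other ERK inhibitors. Escalation rested on DLTs, which are flagged by clinical criteria whatever the PT.

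The argument does not extend to retinal events. Retinal vein occlusion and central serous retinopathy are distinct conditions with different actions in Table 16, and separate PT rows are the informative display.

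Finally, Protocol 10.2 asks investigators to combine signs and symptoms into one diagnosis. This reduces multiple terms within a subject and moves the truth towards the sum of the rows. It does not guarantee that the rows are disjoint, and it does nothing about different investigators choosing different terms for different subjects.

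**Conclusion.** The point holds for rash. The SAP text gives a skin SOC count that is broader than rash and PT rows that are each narrower, and it prespecifies no subject-level rate or worst grade in between. The possible size is a factor of up to about two or three: 21% to 50% affected for rows of 3, 2 and 2 among 14, and at most threefold when three equal terms do not overlap. Under full overlap there is no understatement at all.

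This rests on rash being coded to several PTs, which the protocol's vocabulary makes likely but which no data in the documents demonstrate. It also rests on the separate table specifications containing no grouped row. The SAP agrees with Protocol 11.7 here, nothing is invalidated, and no open decision is shown to depend on it. It is a worthwhile optional improvement.

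**What to change.** In SAP 7.6.2, add a grouped rash row or a short table. List the PTs that make it up, with the MedDRA version, and fix the list before database lock. Count each subject once at worst CTCAE grade, by cohort and for all Phase 2 subjects together. Carry the same row into the summary already planned for events leading to delay, interruption, reduction or discontinuation. Keep the individual PT rows alongside it, since Table 15 treats the rash types separately. Retinal vein occlusion and central serous retinopathy can stay as their own PT rows.

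The cost is one term list and one more table to program; no new data are needed. The drawback is that choosing the PTs takes medical judgement, which is why the list should be settled before lock. If the separate table specifications already contain such a row, a sentence in SAP 7.6.2 pointing to it and to its term list would be enough.

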#### 7.6.3 Dose Limiting Toxicities

DLTs are AEs that occur during the first cycle of treatment and meet 1 or more of the criteria outlined in Section 7.4 of the protocol. The AEs meeting 1 or more of the criteria are indicated on the AE eCRF. The number and percentage of subjects who have DLTs will be summarized by cohort and treatment arm in Phase 1.

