11.7. Safety Analyses

Safety will be assessed by subject-reported and investigator-observed Aes along with concomitant medications, Pes, clinical laboratory tests (hematology, coagulation, serum

chemistry, and urinalysis), vital signs, ECOG performance status, ECGs, and ECHO/MUGA scans.

All Aes will be mapped to the appropriate System Organ Class (SOC) and Preferred Term (PT) according to the Medical Dictionary for Regulatory Activities (MedDRA). Severity of Aes will be graded using CTCAE v4.03 (Appendix 2). All Aes collected during the study will be presented in data listings. TEAEs are defined as events that first occur or worsen after the subject receives study drug on C1D1 until 30 days after the last dose of study treatment, or the start of an alternative anticancer treatment, whichever occurs first, to be defined in more detail in the statistical analysis plan. Summaries will be provided by SOC and PT for all Aes, Aes considered related to study treatment, SAEs, and related SAEs as follows based on the treatment period when the events occur. Similar summaries will also be generated by maximum severity. In addition, exposure to ASTX029, reasons for discontinuation, deaths, and causes of deaths will be tabulated.

The number and proportion of subjects who have DLTs, as defined in Section 7.4, will be summarized by cohort and regimen in Phase 1 Part A.

Laboratory values reported by different local labs will be listed. Shift tables will be provided for each graded laboratory test.

Concomitant medications are the medications taken with a start date on or after the start of the administration of study treatment (C1D1) or those with a start date before the start of the administration of study treatment (C1D1) and a stop date on or after the start of study drug administration (C1D1) as to be defined in more detail in the statistical analysis plan. Concomitant medication will be coded by the World Health Organization (WHO) Global List and summarized by therapeutic subgroup (Anatomical Therapeutic Chemical [ATC] level 2) and PT, sorted alphabetically, using counts and percentages.

Vital sign measurements will be summarized by visit using the proportion of subjects with each vital sign being too high or too low according to conventionally accepted vital sign normal ranges. Physical examination, ECOG performance status, and ECG findings will be listed in data listings or analyzed with summary tables.

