## 3.2 Study Endpoints

## 3.2.1 Primary Endpoint

- Phase 1: Incidences of DLTs and adverse events (AEs) to determine the MTD of up to 2 dosing regimens of ASTX029 and the RP2D and regimen to be taken to Phase 2.
- Phase 2: Clinical activity assessed by ORR according to RECIST v1.1 criteria.

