### 4.0 SAMPLE SIZE

The dose-escalation part of the study (Phase 1 Part A) follows a standard 3+3 study design, with a cohort size of 3 or 6 evaluable subjects. Dose escalation will continue until the MTD for each regimen evaluated is determined. Evaluable subjects for dose-escalation decisions in Part A are those who have completed the first cycle and have received at least 85% of planned doses in the first cycle of treatment (or were not able to receive at least 85% of planned doses due to safety concerns). The final sample size of part A will depend on the assessed dose levels and occurrence of dose limiting toxicities.

For Part B (of Phase 1), a sample size of 14 evaluable subjects will ensure a 90% probability of observing at least 1 adverse reaction to treatment for any adverse reaction with a  $\geq$ 15% incidence. Evaluable subjects for Part B are all subjects who receive any amount of study drug.

For Phase 2, the sample size is based on a Simon's Optimal 2-stage design (Simon 1989). Each cohort will enroll 10 subjects into the first stage. Should  $\geq 2$  first-stage subjects respond, an additional 19 subjects will be enrolled into the second stage. Therefore, up to 29 subjects will be used for each treatment cohort. The sample size, (10+19), or 29, under this Simon's Optimal 2-stage design, will achieve a power of 80% to test the null hypothesis of ORR p0  $\leq 0.1$  at a 1-sided alpha of 0.05 assuming the response rate p1 is 0.3. For Stage 2, the null hypothesis will be rejected if  $\geq 6$  responses are observed in a cohort of 29 subjects. For Cohort F (which will enroll patients with various tumor types and gene aberrations [Protocol Table 2]), the sponsor, with approval of the DSRC, may expand enrollment to 10 or 29 subjects for a particular molecularly defined subpopulation in which the most number of responses are observed, under the same Simon's Optimal 2-stage design as for the other cohorts for better assessment of activity in that disease subpopulation (Optional Cohort F expansion). It is expected that no more than 2 subpopulations will be expanded in this manner.

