## 5.4 Safety Analysis Set

The Safety Analysis Set will include data from all subjects who receive any amount of study drug. Safety analysis will be based on the actual treatment received on Cycle 1 Day 1, which should be the assigned cohort. All data will be included, and no subjects excluded because of protocol violations.

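### SAP 7.6.3 takes its DLT denominator from the Safety Analysis Set, so Part A rates can be reported below those used in the 3+3 decisions

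*SAP*

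**What the plan says.** SAP 3.2.1 gives the Phase 1 primary endpoint as "Phase 1: Incidences of DLTs and adverse events (AEs) to determine the MTD of up to 2 dosing regimens of ASTX029". The table that reports it is specified in SAP 7.6.3: "The number and percentage of subjects who have DLTs will be summarized by cohort and treatment arm in Phase 1". That subsection names no analysis set. Its parent, SAP 7.6, says "Safety Analysis will be performed using the Safety Analysis Set", and SAP 5.4 defines that set: "The Safety Analysis Set will include data from all subjects who receive any amount of study drug".

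The population for dose decisions is different. SAP 4.0, like protocol 11.1, counts as evaluable in Part A "those who have completed the first cycle and have received at least 85% of planned doses in the first cycle of treatment", and adds that subjects who fell short of 85% because of safety concerns also count. This definition is not carried into SAP Section 5, which has no DLT-evaluable set. Protocol 5.4.3 provides for replacing subjects until the planned number of evaluable subjects is reached.

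The protocol does not settle the matter. Protocol 11.7 says DLTs "will be summarized by cohort and regimen in Phase 1 Part A" and gives no denominator. The synopsis places the DLT summary in the same paragraph as the Safety Analysis Set.

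**The concern.** A Part A subject who stops early in Cycle 1 for a reason unrelated to safety, without a DLT, is not evaluable for escalation and is replaced. That subject still took study drug, so the Safety Analysis Set keeps them. In the 7.6.3 table they enlarge the denominator and count as having no DLT, although they were not observed for the full DLT period.

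Subjects who were under-dosed for safety reasons remain evaluable. Those who are in the Safety Analysis Set but not evaluable are therefore mainly DLT-free, and the reported percentage moves downward. At stake is whether the published DLT rate at a dose agrees with the rate on which the escalation rule acted.

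**Working it through.** **Inputs**
- Planned Part A cohort: 3 or 6 evaluable subjects (SAP 4.0, protocol 11.1).
- Decision labels: protocol 7.3.
- Evaluability threshold: 85% of planned doses. In Regimen 1 this is 0.85 × 21 = 17.85, so 18 of 21 doses.
- Number of treated, non-evaluable, DLT-free subjects per cohort, k: not given. Range assumed: 0 to 3.

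**Step 1: reproduce the protocol's percentages.** With r DLTs among n evaluable subjects, the rate is r/n.
- 1/3 = 33.3% (protocol label 33%)
- 2/3 = 66.7% (above 33%)
- 1/6 = 16.7% (below 33%)
- 2/6 = 33.3% (33%)
- 3/6 = 50.0% (above 33%)

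All agree, so the decision rule works on evaluable subjects.

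**Step 2: the same DLTs on the Safety Analysis Set.** The rate becomes r/(n + k).

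| DLTs / evaluable | k = 0 | k = 1 | k = 2 | k = 3 |
|---|---|---|---|---|
| 1/3 | 33.3% | 25.0% | 20.0% | 16.7% |
| 1/6 | 16.7% | 14.3% | 12.5% | 11.1% |
| 2/6 | 33.3% | 28.6% | 25.0% | 22.2% |
| 3/6 | 50.0% | 42.9% | 37.5% | 33.3% |

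At k = 0 the two rates are identical. For any k of 1 or more with at least one DLT, the reported rate is lower.

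**Step 3: can a cohort exceed its planned size?** Protocol 7.1.7 reports one DLT in the 200 mg powder-in-bottle cohort and Cycle 1 Day 1 PK results for nine subjects, so at least nine were treated. With nine treated, the all-treated rate is 1/9 = 11.1%. The number evaluable for DLT is not stated. Over 6, 7, 8 or 9 evaluable, the decision rate would be 16.7%, 14.3%, 12.5% or 11.1%. This shows that a cohort can be larger than six. It does not show that dilution occurred there.

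**Step 4: Part B.** SAP 4.0 counts every treated subject as evaluable in Part B, so the two denominators coincide.

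**The case against.** The strongest reply is that SAP 7.6.3 does not itself name the Safety Analysis Set, that the SAP follows the protocol synopsis, and that the table is descriptive. Counts are shown with percentages, and SAP 7.0 plans listings of study drug administration and adverse events, so a reader could examine exposure. Much of this is fair and limits the consequence. It does not remove the gap: either 7.6.3 inherits the any-dose set, as its position implies, or a primary-endpoint percentage has no defined denominator.

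A reader might infer more than the documents support:
- **That the escalation decisions or the RP2D are compromised.** Protocol 7.3 bases escalation on DLTs and committee review, with evaluability set in protocol 11.1. The RP2D rests on all available PK, biomarker, safety and activity data and has already been chosen. Neither depends on the SAP table.
- **That the 200 mg powder-in-bottle rate is 16.7% and would be misreported as 11.1%.** The nine is a PK count, six evaluable is a guess, and protocol 4.1.1 allows cohort sizes to be changed. All nine may have been evaluable.
- **That the evaluable definition drops subjects who stop in Cycle 1 with a DLT.** The safety-concern clause most naturally keeps them. A strictly literal reading of the completion requirement would exclude them, but that would lower the evaluable rate, the opposite of dilution. It is a reason to word the new set carefully.
- **That the table should be confined to Part A, as in protocol 11.7.** The endpoint is stated for Phase 1 as a whole, and Part B has no denominator problem. The mismatch in scope only needs to be recorded.

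**Conclusion.** The point holds, conditionally. As written, the SAP reports the Part A DLT percentage on all treated subjects, while the 3+3 rule acts on evaluable subjects. In any Part A cohort with a DLT and at least one treated, non-evaluable, DLT-free subject, the reported rate falls below the decision rate. For 2 DLTs in 6 evaluable subjects and an assumed 1 to 3 such subjects, the shortfall is 4.7 to 11.1 percentage points (33.3 − 28.6 to 33.3 − 22.2). With none, it is zero. The documents do not say how many such subjects there are, so the actual size is unknown. The defect is in how a primary endpoint is reported. It should be corrected because following the SAP literally gives the less accurate figure and the remedy is small.

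**What to change.** Add a DLT-Evaluable Set for Part A to SAP Section 5. It should contain treated subjects who meet any one of three conditions:
- they had a DLT in Cycle 1;
- they completed Cycle 1 with at least 85% of planned doses;
- they received less than that because of safety concerns.

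Listing the DLT condition first removes any doubt about subjects who stop early with a DLT.

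In SAP 7.6.3, name this set as the Part A denominator and show the Safety Analysis Set count beside it. For Part B, state that the denominator is all treated subjects. In SAP 7.9, record that the SAP summarizes DLTs across Phase 1 while protocol 11.7 covers Part A only.

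The cost is SAP wording and one population flag. Reported Part A DLT rates may come out slightly higher.
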